- At present, there are inadequate data to correspond frequencies of exacerbations with different levels of asthma severity. In general, more frequent and intense exacerbations (e.g., requiring urgent, unscheduled care, hospitalization, or ICU admission) indicate greater underlying disease severity. For treatment purposes, patients who had ≥2 exacerbations requiring oral systemic corticosteroids in the past year may be considered the same as patients who have persistent asthma, even in the absence of impairment levels consistent with persistent asthma.
- Classifying severity in patients after asthma becomes well controlled, by lowest level of treatment required to maintain control.*

Lowest level of treatment required to maintain control (See figure 4–1b for treatment steps.)	Classification of Asthma Severity			
	Intermittent	Persistent		
		Mild	Moderate	Severe
	Step 1	Step 2	Step 3 or 4	Step 5 or 6

Key: EIB, exercise-induced bronchospasm; FEV₁, forced expiratory volume in second; FVC, forced vital capacity; ICU, intensive care unit

*Notes:

- For population-based evaluations, clinical research, or characterization of a patient's overall asthma severity after control is achieved. For clinical management, the focus is on monitoring the level of control (See figure 3–5b.), not the level of severity, once treatment is established.
- See figure 3–5b for definition of asthma control.

Exclusion Criteria: Receiving albuterol every 4 hours (q4h) at the time of enrollment, concurrent bacterial infection requiring antibiotics, antibiotics received within previous 2 weeks, contraindication to azithromycin (including allergy to macrolides), chronic lung disease other than asthma (including bronchopulmonary dysplasia, cystic fibrosis, bronchiectasis), immunodeficiency (primary or acquired), chronic systemic steroid use, invasive or non-invasive mechanical ventilation required acutely as result of current asthma admission, significant cardiac co-morbidity (including hemodynamically significant cardiac disease or arrhythmia), liver disease (hepatitis), pregnancy, seizure disorder, currently on medication contraindication for use with azithromycin, and/or previous enrollment in study.

Withdrawal from study will occur for:

1. Parent/guardian preference
2. Primary attending preference
3. Worsening of clinical status requiring invasive or non-invasive ventilatory support

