4. Diagnosis of infection requiring antibiotics during the 3-day course of azithromycin/placebo. (However, if the diagnosis of infection and initiation of antibiotics is after the

completion of the 3-day course of azithromycin/placebo, the antibiotic will be recorded and reported. Patients given antibiotics after the completion of the 3-day course of study drug will not be withdrawn from the study and their outcomes will be included in analysis.)

Safety Exit Criteria: Worsening of clinical status requiring invasive or non-invasive ventilatory support

Study Design

This is a double-blind, randomized, placebo-controlled trial. Patients between the ages of 4-12 years of age admitted to the Children's Hospital at Montefiore (CHAM) with an admission diagnosis of asthma exacerbation, as determined by the admitting physician, will be assessed for eligibility within 12 hours of admission by study personnel. Patients may be enrolled in the pediatric emergency room, pediatric inpatient units, or pediatric intensive care unit.

Potential study patients will be identified by the pediatric emergency room staff, pediatric housestaff who will page the research pager upon admission. In addition, attending physicians in the emergency room, pediatric units, and pediatric intensive care unit can refer patients by paging the research paper. Study personnel will review with primary care team any studies (including chest x-ray) that may alter the decision to start antibiotics prior to enrollment in the study. A member of the medical team caring for the patient will approach the parent/guardian and inquire if study personnel can discuss the study with him/her. If a parent/guardian is not available, the research personnel will return when one is available. If the parent/guardian agrees, study personnel will approach him/her and complete a standardized interview to determine if the patient meets eligibility requirements (see Eligibility Questionnaire). If eligibility requirements are met, the research personnel will obtain informed consent from the parent/guardian and assent from the child (if applicable) for participation in the study. If a female patient has achieved menarche, a pregnancy test will be administered with the consent of the parent/guardian and assent of the patient. Pregnant patients will be excluded from the study.

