The research personnel will then conduct a standardized interview to obtain baseline demographic, clinical, and contact information from the parent/guardian (see Enrollment Questionnaire).

The enrolled patient will then be randomized by the Pharmacy Investigational Drug Services. Patients will either receive azithromycin suspension or indistinguishable placebo suspension once daily for three days at a dose of 10 mg/kg/dose with a maximum dose of 500 mg/dose. All research personnel, medical staff, patients, and parents/guardians will be blinded to the composition of suspension prepared in the research pharmacy. If the patient is discharged before the third dose of medication is administered, the pharmacy will provide any remaining suspension doses to be completed by patient as an outpatient.

The selection of the intervention dose of azithromycin (once daily dosing of 10 mg/kg/dose with a maximum dose of 500 mg) was made for several reasons. This dosing is shorter and more convenient to administer than the more commonly used 5 day course with 10 mg/kg/day for one day and 5 mg/kg/day for subsequent days. Since the average length of stay for patients 4-12 years old with asthma is 3 days, it is more likely that patients will complete this dosing during hospitalization. This dosing is currently recommended for other infectious indications including otitis media in penicillin allergic patients. In addition, this dosing is consistent with an open trial registered at clinicaltrials.gov in Denmark studying azithromycin treatment in children 1-3 years of age with recurrent asthma (planned enrollment November 2010 until November 2014).

At the time of enrollment, the patient will have an asthma severity score performed by research personnel via the Pediatric Asthma Severity Score (PASS), which has been validated in children 1-18 years old.^{37,38} The score will be conducted within 30 minutes prior a scheduled beta-agonist treatment or at any time if patient is on continuous albuterol. This score will be used to determine severity of the patient's asthma exacerbation at the time of enrollment.

Pediatric Asthma Severity Scoring (PASS)

Signs	0	1	2
Wheezing (= expiratory sounds heard auscultation)	None/mild	Moderate	Severe or absent due to poor air entry
Respiratory work (= utilization of accessory muscles or retractions)	None/mild	Moderate	Severe

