The primary outcome measure is hospital length of stay (LOS). Preliminary data obtained from a Clinical Looking Glass search reveals that in 2011, there were 410 children between the ages of 4-12 years admitted to CHAM with a primary diagnosis of asthma. During their admission, 237 patients received inhaled steroids, a marker of a persistent asthma diagnosis. Using this data, the mean length of stay was 3.0 days, median 2.5 days, and standard deviation 1.6. The distribution approximated normal distribution in this group. A clinically significant difference in length of stay would be 16 hours or 0.67 days (equivalent to 0.4 standard deviations).

Data analysis will be conducted with the assistance of a statistician. LOS between the two groups will be compared using independent samples t-test, if the data is normally distributed. If the data is not normally distributed, log transformation will be attempted and if the results of the transformation yield normal distribution for both groups, then t-test will be used for the logged values and reported as a geometric mean. If log transformation is not successful in yielding normal distribution, non-parametric Mann-Whitney U test will be used to report median and interquartile ranges. All tests will be two-tailed with an $\alpha = 0.05$ to denote clinical significance.

In order determine the number of patients needed to enroll to detect a 16 hour (0.67 day) difference in length of stay with a power of 80%, PASS software was utilized, with the assistance of a statistician, to model various types of adjustments for non-parametric distribution –normal distribution adjustment, uniform distribution adjustment, and logistic distribution adjustment. For each of these adjustments, the number of patients required for enrollment per

group ranged from 83 to 96 patients. Using the largest number, 96, and assuming a 10% attrition rate for parent/guardian preference, attending preference, or safety exit criteria, the sample size will need to be 107 patients in each group. We anticipate it will take approximately 15-18 months to enroll this number of patients.

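### Needing ventilatory support withdraws a child from the study, and nothing keeps that child's length of stay in the primary analysis, so harm in the arm with more such children can be hidden

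*Combined protocol and SAP*

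**What the plan says.** In the combined protocol and SAP, the Population section introduces its list with "Withdrawal from study will occur for". Item 3 is "Worsening of clinical status requiring invasive or non-invasive ventilatory support". The Safety Exit Criteria repeat it, and so does the withdrawal paragraph under Adverse Event Monitoring. None of these places limits the rule to stopping study drug, and none sets a time limit, so a child ventilated after the third dose is also withdrawn.

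The entry criteria exclude children with "invasive or non-invasive mechanical ventilation required acutely as result of current asthma admission". Under Study Design, randomisation follows enrolment: "The enrolled patient will then be randomized by the Pharmacy Investigational Drug Services". For an enrolled child the exit is therefore a new deterioration, in practice after randomisation.

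The Statistical Analysis section raises 96 evaluable children per group to 107, "assuming a 10% attrition rate for parent/guardian preference, attending preference, or safety exit criteria".

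Only one group has its outcomes expressly kept. Item 4 withdraws a child for "Diagnosis of infection requiring antibiotics during the 3-day course of azithromycin/placebo", but those given antibiotics after the course "will not be withdrawn from the study and their outcomes will be included in analysis". The document defines no intention-to-treat or other analysis set, has no missing-data rule, and does not say that length of stay or follow-up is collected after withdrawal.

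**The concern.** A ventilated child has failed to recover, and recovery is what length of stay is meant to capture. Taking such children out of the comparison conditions the primary analysis on something that happens after randomisation and that treatment may influence. The Risks/Benefits section itself allows that azithromycin might make some children worse and lengthen their stay. If it did so through ventilatory support, the withdrawal rule would remove the very children who show it.

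The event is plausible in this trial. Children can be enrolled in intensive care, some will be on continuous albuterol, and non-invasive support counts. Reporting withdrawal reasons by arm would show how many children left, but would not return their stays to the primary comparison.

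**Working it through.** **The plan's own sample size.** Inputs from Statistical Analysis: difference 0.67 days, SD 1.6 days, two-sided alpha 0.05, power 80%. The standardised difference is 0.67/1.6 = 0.419, and a two-sample t-test needs 90.5 per group. Dividing by the Mann-Whitney relative efficiency gives 83 (logistic, π²/9), 91 (uniform, 1) and 95–96 (normal, 3/π, depending on rounding). This matches the stated range of 83 to 96. Then 96/0.9 = 107. The arithmetic is sound. It also shows where safety exits sit: among the children who separate 107 enrolled from 96 evaluable.

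**Are withdrawn children out of the analysis?** Three places point that way.
- The sentence on later antibiotics pairs not being withdrawn with being analysed. Ventilated children are on the other side of that pairing.
- Length of stay should be available from the hospital record. Counting a ventilated child as attrition makes sense only if the child leaves the comparison.
- Study Design says that no medical treatment excludes a child from the study, then sets ventilatory support apart as a safety exit.

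None of them states exclusion.

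**Size of the shift.** Suppose one arm has k more ventilated children than the other, each staying L days, and all other children average 3.0 days. Dropping the extra children lowers that arm's mean by

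k × (L − 3.0)/107 days.

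Inputs: the planning group ("the mean length of stay was 3.0 days, median 2.5 days, and standard deviation 1.6"); L = 5.0 days, the mean for asthma patients transferred to intensive care (Azithromycin and Asthma at CHAM), as a proxy; k = 3, assumed.

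- Raw means: 3 × 2.0/107 = 0.056 days = 1.35 hours; 1.35/16 = 8.4% of target. One child gives 0.45 hours.
- Log scale: a lognormal with mean 3.0 and SD 1.6 has mu 0.973 and sigma 0.500. The 16-hour target is ln(3.0/2.333) = 0.2513. The shift is 3 × (ln 5.0 − 0.973)/107 = 0.0178, or 7.1% of target.
- Rank scale: the target is Φ(0.2513/(0.500√2)) − 0.5 = 0.1388. The shift is 3 × (0.898 − 0.5)/107 = 0.0112, or 8.0% of target.

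For scale, the standard error of the raw difference is 1.6 × √(2/107) = 0.219 days = 5.25 hours. If ventilation rates are equal, k = 0 and there is no shift.

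**Range over assumed rates.** The shift in means is (difference in ventilated share) × (excess stay). All rates and excesses here are assumptions.

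| Ventilated, arm A v arm B | Excess 2 days | Excess 3 days |
|---|---|---|
| 5% v 2% | 0.06 days (9% of 0.67) | 0.09 days (13%) |
| 10% v 5% | 0.10 days (15%) | 0.15 days (22%) |

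**What is lost.** In a simulation with 107 per arm, normal stays (mean 3.0, SD 1.6), 3 extra days for ventilated children and no other difference, the chance of a significant result showing the longer stay in the worse arm was:
- 5% v 2% ventilated: 5.4% with all children analysed, 2.8% with ventilated children dropped;
- 10% v 2% ventilated: 17% with all analysed, 2.4% with them dropped.

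Chance alone gives 2.5% in that direction. Dropping these children removes essentially all ability to see this kind of harm in length of stay, though at the smaller imbalance there was little to begin with.

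**Power after the fix.** With the 3/π efficiency factor, power for 0.67 days is 81% with 96 per group and 85% if all 107 are analysed.

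**The case against.** Exclusion is inferred. The sentence on later antibiotics was written to separate two kinds of antibiotic use and does not address ventilation, and the 10% is a planning allowance, not an analysis-set definition. This stands, and it is why the point is put as the natural reading and not as a stated rule. If the sponsor always meant to analyse these children, the same added sentence settles it.

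The size rests on weak inputs. The 5.0-day figure covers asthma patients transferred to intensive care in 2008–2010, not ventilated children aged 4–12 with persistent asthma, and setting it against 3.0 days from 2011 mixes populations. The broader 2010 figures in the same section imply an overall mean of 0.14 × 4.5 + 0.86 × 3.2 = 3.4 days. An excess of 1.6 days would make the three-child shift 3 × 1.6/107 = 0.045 days = 1.1 hours, or 6.7% of target. This also stands: the size is unknown and may be small.

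Safety is partly covered. Worsening and intensive-care transfer are monitored as adverse events, and the monitoring board receives data every three months. An excess of ventilation could be noticed there, but that does not repair the primary comparison.

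A reader might go further and infer that the rule inflates the false-positive rate, so that azithromycin could be declared effective when it is not. The documents do not support that. If the drug does nothing, or if it leads to ventilation in a few children and leaves the rest alone, the retained children remain comparable between arms and the error rate stays near 5%. Obtaining inflation requires equal full-arm stays despite the imbalance, with the other children in that arm staying shorter by exactly the offsetting amount. False benefit could arise if the drug led to ventilation in children who would have stayed long anyway, but nothing in the documents quantifies that.

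**Conclusion.** The concern holds as a flaw in the withdrawal rule. Followed as written, it takes children out of the study after randomisation for an event tied to the primary outcome, and the plan treats them as attrition. The main risk is masked harm: the arm with more ventilated children looks better than its full randomised result, which is not the same as looking better than the other arm.

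The effect on the estimate is probably small: about 1.3 hours, or 7–8% of the 16-hour target, for an assumed imbalance of three children at the 5.0-day proxy. It is larger only with greater imbalance or longer stays, for neither of which the documents give a figure. No false-positive rate should be attached to this point, and it should not be said that the protocol states these children are excluded. The sample-size calculation is not at fault. This should be changed because the remedy is cheap and standard, with medium confidence given the inference and the unknown event rate.

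As a secondary matter, attending-preference withdrawals and antibiotics started during the course leave the same gap. The on-course antibiotic reason is also missing from the withdrawal paragraph under Adverse Event Monitoring and from the attrition reasons in Statistical Analysis.

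**What to change.** Amend the withdrawal list, the Safety Exit Criteria and the withdrawal paragraph under Adverse Event Monitoring to one common rule, for example:

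*Ventilatory support at any time stops any remaining study drug only. The child stays in the study. Length of stay, adverse events and both follow-up calls are collected and analysed in the randomised arm unless the parent withdraws consent to data collection. Ventilatory support is reported by arm.*

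Apply the same retention of length of stay to attending-preference withdrawals and to antibiotics started during the course, and make the lists of reasons agree across sections.

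The cost is one wording amendment and a few extra follow-up calls to families of very ill children. The event is already identified because it triggers the exit, and length of stay should be obtainable from the hospital record, although the protocol does not describe how it is captured. Enrolment of 107 per arm can stay.

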Prolongation of expiration (= ratio of the length of expiration over inspiration)	Normal/mild prolongation	Moderate prolongation	Severe prolongation

Other than the administration of azithromycin suspension or placebo, the medical treatment of the enrolled patients will be at the discretion of the medical team. The current standard of care for treatment of acute asthma exacerbations in hospitalized children includes inhaled beta-agonists and systemic steroids. The medical team often continues or initiates "controller" asthma medications during the inpatient stay (ie inhaled corticosteroids, leukotriene receptor antagonists). In addition, patients with severe asthma might receive intravenous medications (ie magnesium sulfate, terbutaline, aminophylline). No medical treatments will constitute exclusion from the study. However, invasive or non-invasive mechanical ventilatory support will be part of safety exit criteria.

At 7-10 days and again between 28 and 35 days after discharge, research personnel will contact the parent/guardian of enrolled patient for a follow-up interview. This interview will include questions about recurrence of asthma symptoms, days of work/school missed, hospital readmissions, emergency room visits, pediatrician visits, subsequent steroid courses, and medication side effects.

Mechanism Subset Study: A Pilot and Feasibility Study in a Subset of Patients

After enrollment, and at the time of the PASS asthma severity scoring, research personnel will ask parents/guardians if they would also be willing to participate in a separate subset study involving blood and nasal aspirate samples. If parents/guardians consent, they will be offered compensation for their time and inconvenience (if funding is available). If the parent/guardian is interested, the research personnel will obtain a separate, additional informed consent from the parent/guardian and assent from the child for the "Mechanism Subset Study". At that time, a nasal aspirate sample will be obtained by the research personnel (who will be trained on proper technique prior to the start of study). A blood sample will be obtained as soon as possible. A second sample of both blood and nasal aspirate will be obtained on the calendar day that is 48 hours from the first sample. Two samples will allow for baseline and post-treatment samples to be compared.

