The intervention medication, azithromycin, is a relatively commonly used antibiotic in the pediatric population for a variety of illnesses, including otitis media, atypical pneumonia, and pharyngitis. It is relatively well tolerated. The major side effects are gastrointestinal and temporary. Other side effects, including elevation of hepatic enzymes and prolonged QT syndrome, are rarely reported (less than 1%) and considered unlikely by the investigators. Patients will be monitored by the primary medical team for symptoms of rare and common side effects and will inform the PI of any concerns. Education will be conducted on pediatric units and in the critical care unit regarding side effects to ensure adequate monitoring by the primary medical teams. There is little clinical evidence on the use of azithromycin in children hospitalized with acute asthma, therefore it is possible that azithromycin will worsen the condition of some patients and increase length of stay. Previous studies in long-term macrolide use have shown either clinical improvement or no effect and none have reported any significant harm.

The alternative treatment for children hospitalized with acute asthma is the current standard of care: inhaled beta-agonists and systemic steroids. All patients enrolled, at the discretion of the attending physician and medical team, are expected to receive these treatments in addition to the study medication.

The potential benefit of this study to research participants is that azithromycin may decrease length of stay in the hospital and days of symptoms. In addition, it may have longer-term effects and decrease rate of readmission to the hospital or subsequent medical visits or steroid courses in the month following administration.

Protections Against Risk

All patients will be hospitalized at the Children's Hospital at Montefiore (CHAM), a 120-bed tertiary level pediatric hospital well equipped for the management of children with acute respiratory illnesses, including severe asthma. Clinical risks to patients will be protected by close clinical monitoring for patients who meet exit criteria of mechanical ventilation. In the event of an adverse event to a patient enrolled in the study, the patient will be assessed by the attending physician, research investigator, and/or the Pediatric Rapid Response Team (PMET) or pediatric code team.

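### No analysis set is defined and children withdrawn after randomization appear to leave the length-of-stay comparison, which can bias the primary estimate

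*Combined protocol and SAP*

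**What the plan says.** METHODS lists four reasons for withdrawal from the study, all of which can arise after randomization. Two are preferences (parent or guardian, attending physician). Two are clinical events: "Worsening of clinical status requiring invasive or non-invasive ventilatory support" and "Diagnosis of infection requiring antibiotics during the 3-day course of azithromycin/placebo". A parenthesis under the second adds that children whose antibiotics start after the course is complete "will not be withdrawn from the study and their outcomes will be included in analysis". No other sentence in the document says whose outcomes are analysed.

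STATISTICAL ANALYSIS gives the primary test without naming a population: "LOS between the two groups will be compared using independent samples t-test, if the data is normally distributed", with a log-scale t-test or a Mann-Whitney test as fallback. The sample size goes from 96 to 107 per group, "assuming a 10% attrition rate for parent/guardian preference, attending preference, or safety exit criteria".

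The lists of reasons do not agree. In-course infection is item 4 of the METHODS list. It is missing from the withdrawal list under Adverse Event Monitoring and from the attrition reasons in STATISTICAL ANALYSIS. Study Design says of enrolled patients "No medical treatments will constitute exclusion from the study" and names only ventilatory support as an exit.

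**The concern.** The parenthesis promises analysis to a group because it is not withdrawn, and the attrition allowance counts preference withdrawals and safety exits as lost to the LOS test. Together these imply that withdrawn children are left out.

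Two of the withdrawal reasons are outcomes of the illness under treatment or its course. A child who comes to need ventilation has worsened and is likely to stay longer. The study drug is itself an antibiotic, so in-course infection could differ by arm. Risks/Benefits concedes that "it is possible that azithromycin will worsen the condition of some patients and increase length of stay", while noting that earlier long-term studies reported no significant harm. A comparison that drops such children cannot fully show a harm of that kind, or a benefit from preventing these events.

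If the extra stay per event is similar in both arms, exclusion understates the benefit when azithromycin prevents events and flatters the drug when it causes them. With no written rule, the set could also be chosen after the withdrawals are known.

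Only the LOS estimate is at stake. Intensive-care transfer and clinical worsening are monitored separately, and a monitoring board reviews safety every 3 months.

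**Working it through.** **The plan's own sample size.** Inputs from STATISTICAL ANALYSIS: difference 0.67 day, SD 1.6, two-sided 5%, power 80%. A two-sample t-test needs 90.5, so 91 per group. Dividing 91 by the Mann-Whitney relative efficiency gives:
- logistic (π²/9): 83
- uniform (1): 91
- normal (3/π): 96

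This matches the stated range of 83 to 96. Then 96/0.9 = 106.7, rounded up to 107. The arithmetic is right, and 107 − 96 = 11 children per arm are allowed to leave the comparison.

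**Bias formula.** In one arm, let p be the share withdrawn for ventilation or in-course infection, D the extra days those children stay, and m the mean LOS of the others. The mean over all randomized children is m + pD; exclusion leaves m. The placebo-minus-azithromycin difference is therefore understated by

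p(placebo) × D(placebo) − p(azithromycin) × D(azithromycin),

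and a negative value means it is overstated. Withdrawals unrelated to LOS do not change this.

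**Inputs.** The documents give no event rates by arm and no LOS for withdrawn children, so every p and D below is an assumption. D = 2 has a rough anchor: mean LOS was 5.0 days for intensive-care transfers (Azithromycin and Asthma at CHAM) against 3.0 days in the planning data, although the populations differ and transfer is not ventilation. D = 4 has no anchor.

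| Placebo v azithromycin | D (days) | Understatement (days) | Share of 0.67 | Estimate if truth is 0.67 |
|---|---|---|---|---|
| 2% v 1% | 2 | 0.04 − 0.02 = 0.02 | 3% | 0.65 |
| 4% v 2% | 2 | 0.08 − 0.04 = 0.04 | 6% | 0.63 |
| 4% v 2% | 4 | 0.16 − 0.08 = 0.08 | 12% | 0.59 |
| 5% v 2% | 4 | 0.20 − 0.08 = 0.12 | 18% | 0.55 |
| 6% v 1% (extreme) | 4 | 0.24 − 0.04 = 0.20 | 30% | 0.47 |
| 2% v 5% | 4 | 0.08 − 0.20 = −0.12 | −18% | 0.79 |

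Equal rates of 3% with D = 4 on placebo and 2 on azithromycin give 0.12 − 0.06 = 0.06 day. Equal rates with equal D give zero.

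**Simulation.** The last column was confirmed with 107 per arm, lognormal LOS plus D for an event, placebo mean 3.0 and SD 1.6, and 5–8% random withdrawals (20,000 replicates). If the drug acts only through these events (5% v 2%, D = 4), the difference is 0.12 day with all randomized children and 0.00 after exclusion. With an inert drug the test rejected in 4.6–4.9% of trials, and in 4.9% when 10% per arm were all withdrawn from the longest quarter of stays.

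**The case against.** - **Exclusion is inferred.** The parenthesis clarifies one subgroup, the two groups in the test could mean the groups as randomized, and follow-up calls are planned without excepting withdrawn children. This stands as a limit on certainty. But the plan counts safety exits as attrition, and follow-up calls do not define an analysis set. On any reading the rule is missing.
- **The bias may be small.** At D = 2, the value nearest to the documents' figures, the illustrations give 0.02 to 0.04 day, about 0.5 to 1 hour. Events should be uncommon because children already ventilated or needing antibiotics are excluded at entry. This stands.
- **The formula covers the arithmetic mean only.** The plan may instead report geometric means or medians. For 5% v 2% with D = 4, the shift is 0.12 day in the mean, about 0.08 in the geometric mean and 0.05 in the median. This stands and lowers the stakes under the fallback analyses.
- **Direction is not fixed.** Fewer but longer events on azithromycin could reverse it. True; the formula shows that p × D in each arm decides.
- **Blinding protects the comparison.** "All research personnel, medical staff, patients, and parents/guardians will be blinded to the composition of suspension", and with an inert drug the 5% level holds. That protects the test under no effect. It does not protect the estimate if the drug acts on these events.
- **Study Design is a weak contradiction.** Its sentence follows a list of asthma treatments and need not cover antibiotics for a new infection. Agreed; the clearest mismatch is with the Adverse Event Monitoring list.

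**Conclusion.** The concern holds and should be fixed, though it is not fatal to the trial. It is certain that the plan states no analysis set and no rule for LOS after withdrawal. That withdrawn children would be left out is the most natural reading, not an explicit statement. The resulting bias is conditional on azithromycin changing the frequency of ventilation or in-course infection, or the kind of child affected. Confidence in its size is low: under the assumed inputs it runs from 0.02 to 0.12 day in the moderate cases and 0.20 day in the extreme one, in either direction. These are illustrations, not bounds. The disagreement over in-course infection needs resolving whatever the size.

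**What to change.** State in STATISTICAL ANALYSIS that the primary comparison includes every randomized child in the assigned arm. LOS to hospital discharge should come from the hospital record regardless of stopping study drug, ventilation or antibiotics, except where consent to further data use is refused or withdrawn. State how LOS missing for that reason is handled. Report withdrawals by arm and reason, and give the analysis without withdrawn children as a sensitivity analysis. Leave the clinical stopping rules as they are. Reconcile the METHODS withdrawal list, Study Design, the attrition reasons and the Adverse Event Monitoring list on in-course infection.

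The cost is wording, plus a check that consent permits use of the hospital record after withdrawal; the consent pages are not in the copy reviewed. The sample size need not change.

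The downside is possible dilution by children who stopped study drug. At 0.67/1.6 = 0.419 SD:
- **107 per arm, no dilution:** power is 86.2% (t-test) or 84.6% (Mann-Whitney, normal shape), against 82.3% or 80.5% with 96.
- **107 per arm, 10% of children with no benefit (assumed; 0.67 × 0.9 = 0.603 day):** 78.4% or 76.5%. Power stays at 80% up to about 8% or 6% dilution.
- **5% refusing data use (assumed; 107 × 0.95 = about 102 per arm):** about 84% or 83% before dilution, so those margins shrink.
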